**7.3.2.3. Jump to Reference (J2R) - Using On and Off-treatment Data**

All exacerbations (on and off-treatment) will be analysed with a J2R missing data sensitivity analysis as for on-treatment exacerbations. Here however, the unobserved period will be defined for subjects that prematurely withdraw from the study from the date of study conclusion up to the projected Week 52 date (see Section 11.5.1.4). Thus, all exacerbations observed in the study will be included in this analysis, not just on-treatment exacerbations.

**8. SECONDARY EFFICACY STATISTICAL ANALYSES**

**8.1. Overview of Planned Efficacy Analyses for Secondary Endpoints**

The secondary efficacy analyses will be based on the ITT population. Since off-treatment data was not collected for Trough FEV1 and SGRQ, all analyses for these endpoints will use on-treatment data only.

[Table 4](#) provides an overview of the planned secondary efficacy analyses, with the detailed list of data displays being presented in Section 11.12.

**Table 4 Overview of Planned Efficacy Analyses**

	Absolute							Change from Baseline						
	Stats Analysis			Summary		Individual		Stats Analysis			Summary		Individual	
	T	F	L	T	F	F	L	T	F	L	T	F	F	L
Trough FEV1														
Baseline FEV1				Y			Y							
Trough FEV1	Y 			Y			Y	Y 	Y 		Y			Y
Sensitivity Analysis: Trough FEV1, imputing data following FF/UMEC/VI	Y 							Y 	Y 					

	Absolute							Change from Baseline						
	Stats Analysis			Summary		Individual		Stats Analysis			Summary		Individual	
	T	F	L	T	F	F	L	T	F	L	T	F	F	L
discontinuation using jump to reference assumption														
SGRQ Total Score														
Baseline SGRQ Scores				Y			Y							
SGRQ Total Score	Y 			Y 			Y 	Y 	Y 		Y 	Y 		Y 
SGRQ Individual Item Responses							Y							
Sensitivity Analysis: SGRQ Total Score, imputing data following FF/UMEC/VI discontinuation using jump to reference assumption	Y 							Y 	Y 					
COPD Exacerbations														
Time to First On-treatment Moderate/Severe Exacerbation	Y 	Y 		Y	Y 									
Sensitivity Analysis: Time to First Moderate/Severe Exacerbation Including Off-treatment Data	Y 	Y 			Y 									
Sensitivity Analysis: Time to First On-treatment Moderate/Severe Exacerbation or treatment discontinuation	Y 	Y 			Y 									
Time to First On-treatment Moderate/Severe Exacerbation by Eosinophil Subgroup	Y 	Y 		Y	Y 									
Annual Rate of On-treatment Moderate/Severe Exacerbations by Eosinophil Subgroup	Y 	Y 												

	Absolute							Change from Baseline						
	Stats Analysis			Summary		Individual		Stats Analysis			Summary		Individual	
	T	F	L	T	F	F	L	T	F	L	T	F	F	L
Annual Rate of On-treatment Severe Exacerbations	Y 	Y 		Y										

**NOTES :**

- T = Table, F = Figure, L = Listing, Y = Yes display generated.
  - Stats Analysis = Represents TFL related to any formal statistical analyses (i.e. modelling) conducted.
  - Summary = Represents TFL related to any summaries (i.e. descriptive statistics) of the observed raw data.
  - Individual = Represents FL related to any displays of individual subject observed raw data.
1. Mixed Models Repeated Measures (MMRM) analysis
  2. Least squares (LS) means (95% CI) change from baseline and LS mean (95% CI) treatment differences
  3. Box plot and empirical distribution function plot at Week 52
  4. Cox proportional hazards analysis
  5. Kaplan-Meier plot displaying FF/UMEC/VI, FF/VI and UMEC/VI and repeated displaying FF/VI and UMEC/VI only
  6. Plot of hazard ratios (95% CI)
  7. Negative binomial regression model
  8. Plot of on-treatment adjusted exacerbation rate ratios
  9. Summary and listing will include all individual SGRQ domain scores as well as the SGRQ total score
  10. Analysis of Covariance (ANCOVA). This analyses will be performed twice; once using FF/VI as the reference group and a second time using UMEC/VI as the reference group
  11. LS mean (95% CI) treatment differences at Week 52 for both the primary and all sensitivity analyses for each endpoint separately to be included as a forest plot
  12. Hazard ratios (95% CI) for both the primary analyses and all sensitivity analyses to be included as a forest plot
  13. Additional plot of LS means (95% CI) change from baseline for UMEC/VI and FF/VI treatment groups only

**8.2. Trough FEV1 and SGRQ Total Score**

**8.2.1. Planned Primary Statistical Analyses for Trough FEV1 and SGRQ Total Score**

Secondary Statistical Analyses
Endpoint(s)

 
• Change from baseline in trough FEV1
 
• Change from baseline SGRQ total score
 

Model Specification

 
• Mixed Models Repeated Measures (MMRM) model.
 
• While missing data are not explicitly imputed in the primary MMRM analyses, there is an underlying assumption that the data are missing at random. All available scheduled post-baseline assessments will be utilized and via modeling of the within-subject correlation structure, the derived treatment differences will be adjusted to take into account missing data.
 
• The MMRM analysis for trough FEV1 will include on-treatment FEV1 measurements at Weeks 4, 16, 28, 40 and 52. The MMRM analysis for SGRQ total score will include on-treatment SGRQ total scores at Weeks 4, 28 and 52.
 
• Although the secondary endpoints are Change from baseline in trough FEV1 at Week 52 for
 

Secondary Statistical Analyses

FF/UMEC/VI vs. FF/VI and Change from baseline in SGRQ total Score at Week 52 for FF/UMEC/VI vs. FF/VI, results for all treatment comparisons at all time points where data are scheduled to be collected will be included in the analysis and presented in the displays.
 
 
• Terms in the model: 
 
• Response: trough FEV1 or SGRQ Total score at each visit.
 
• Categorical: treatment group, smoking status (screening), geographical region, visit
 
• Continuous: baseline FEV1 or baseline SGRQ Total score
 
• Interaction: baseline*visit, treatment group*visit
 
• Repeated: visit
 
 
 
• The model will be fit with an unstructured variance-covariance matrix.
 
• The Kenward and Roger method (KR) for approximating the denominator degrees of freedom and correcting for bias in the estimated variance-covariance of the fixed effects will be used. In the event the model fails to run using the KR method, then the residual method will be used instead.
 
• Baseline is defined in Section 11.4.2
 
• Two models will be fitted; one with a response variable of change from baseline and one with the response variable as the raw value.
 

Model Checking & Diagnostics

 
• Refer to Appendix 10: Model Checking and Diagnostics for Statistical Analysis.
 

Model Results Presentation

 
• Least-square (LS) means and LS mean change from baseline values for each treatment group will be presented with their associated standard errors as well as 95% CIs. The estimated treatment difference along with corresponding standard error, 95% CI for each Week will be presented.
 
• Both adjusted (accounting for the Hochberg multiplicity adjustment, see Section 11.9) and unadjusted p-values will be presented for the pairwise treatment comparison at Week 52 of FF/UMEC/VI versus FF/VI. Unadjusted p-values only will be presented at other visits for the comparison of FF/UMEC/VI versus FF/VI and at all visits for the treatment comparisons of FF/UMEC/VI versus UMEC/VI and UMEC/VI versus FF/VI.
 
• The LS mean treatment differences (and associated 95% CIs) for all weeks will also be presented graphically for FF/UMEC/VI versus FF/VI and FF/UMEC/VI versus UMEC/VI.
 
• The LS mean change from baseline values (and 95% CIs) for the three treatment groups across weeks will be presented and repeated displaying the FF/VI and UMEC/VI treatment groups only.
 

Example SAS Code
<pre>proc mixed data=dsetin;   class trtcd visit subjid smk region;   model endpoint=trtcd baseline smk region visit visit*baseline visit*trtcd / ddfm =kr;   repeated visit / subject=subjid type=un;   lsmeans trtcd*visit / cl diff e om=OMdset at (baseline)=(&blm.);   ods output lsmeans=lsmeans;   ods output diffs=diffs;</pre>

**Secondary Statistical Analyses**

*run;*

[where Omdset is a dataset with a row for every subject-visit combination that contains all of the covariates and blm is a macro variable containing the mean baseline for the subjects used in the analysis. This is used to derive the LS means using coefficients which are based on the subjects used in the analysis.]

**8.2.2. Planned Sensitivity Statistical Analyses for Trough FEV1 and SGRQ Total Score****8.2.2.1. Jump to Reference - Using On-treatment Data**

On-treatment trough FEV1 will be analysed in a sensitivity analysis to examine the robustness of the FEV1 analysis to departures from the implicit assumption that missing data is missing-at-random (MAR).

Subjects with missing on-treatment FEV1 data will have their “missing” data imputed and the Week 52 data (actual or imputed) will be analysed.

The jump-to-reference (J2R) multiple imputation method is based a pattern mixture model fully described by [[Carpenter et al, 2013](#)].

First the on-treatment MMRM analysis is run so that samples of all the model parameters i.e. the estimated “betas” associated with treatment, gender, exacerbation history, etc., and the estimated variance and covariance parameters can be taken (from their joint posterior distribution). From each sample it is possible to construct a mean for any subjects with “missing” data. In the J2R method, the mean estimate is constructed using the estimated beta associated with the reference treatment, as well as all the subject’s other covariates. This estimated mean together with the sampled estimated variance parameters makes it possible to sample from a normal distribution for the trough FEV1 at a particular missing visit. First however, the unconditional distribution is updated using the appropriate conditional distribution algebra and the subject’s own observed data. Then the sample is taken using the conditional normal distribution parameters.

The Week 52 data from each sample (imputed for some subjects, and non-missing for most subjects) is analysed using an ANCOVA model using the same covariates as the original model of FEV1 (with the exception of the visit covariate and its interactions). The results from the analyses of each sample are combined using Rubin’s formulae [[Rubin, 1987](#)] as implemented in PROC MIANALYZE in SAS.

Jump-to-reference might be considered a worst case scenario which is likely to give a conservative estimate of treatment effect because the missing data is assumed to follow the same ‘reference pattern’ in all subjects regardless of their study treatment.

This J2R sensitivity analysis will be repeated twice, once using the FF/VI treatment group as the reference, and once using the UMEC/VI treatment group as the reference. However note that in both models, data from all treatment groups will be used in the model, but only one comparison will be presented.

SGRQ will be analysed in exactly the same way.

Sensitivity Statistical Analyses – Jump to Reference
Endpoint(s)

 
• Change from baseline in trough FEV1
 
• Change from baseline SGRQ total score
 

Model Specification, Checking & Diagnostics, Results Presentation and SAS Code

 
• Analysis of Covariance (ANCOVA) model using data generated from multiple imputation methods and the same covariates as the original model (except visit and its interactions).
 
• Analysis model and results presentation will be the same as described in Section 8.2.1, but imputing for missing data as described above using the Jump to Reference method and only presenting unadjusted p-values.
 

### 8.3. Time to First COPD Moderate/Severe Exacerbation

#### 8.3.1. Planned Primary Statistical Analyses for Time to First On-treatment Moderate/Severe Exacerbation

Secondary Statistical Analyses
Endpoint

 
• Time to first on-treatment moderate/severe exacerbation
 

Model Specification

 
• Cox's proportional hazards model
 
• Terms in the model: 
 
• Response: time to first on-treatment, moderate/severe exacerbation
 
• Categorical: treatment group, gender, exacerbation history (<math>\leq 1</math>, <math>\geq 2</math> moderate/severe), smoking status (screening), geographical region
 
• Continuous: post-bronchodilator % predicted FEV1 (Screening)
 
 
 
• The 'exact' method will be used for handling ties. If the analysis will not run using the 'exact' method, then the 'Efron' method for handling ties will be used instead.
 
• Kaplan-Meier survivor functions will be obtained for each treatment group using PROC LIFETEST with a TIME statement.
 

Model Checking & Diagnostics

 
• Refer to Appendix 10: Model Checking and Diagnostics for Statistical Analysis
 

Model Results Presentation

 
• Hazard ratios and the percent reduction in risk for the pairwise treatment comparisons with associated 95% CIs and p-values will be presented.
 
• Both adjusted (accounting for the Hochberg multiplicity adjustment, see Section 11.9) and unadjusted p-values will be presented for the pairwise treatment comparisons of FF/UMEC/VI versus FF/VI and FF/UMEC/VI versus UMEC/VI. Only unadjusted p-values will be presented for the treatment comparison of UMEC/VI versus FF/VI. The probability of having a moderate/severe exacerbation, 95% CI and first quartile and median time to exacerbation for each treatment group will be presented.
 
• The Kaplan-Meier curves will be presented showing the probability of having an event over
 

time for each treatment group separately plotted on the same figure. This will be repeated displaying UMEC/VI and FF/VI only.
Example SAS Code
<pre>proc phreg data=dsetin;   class trtcd smk region exachis gender;   model timeto1*eventflag(0) = trtcd smk region gender pctpredFEV exachis/ risklimits   ties=exact;   hazardratio trtcd / diff=all; run;  proc lifetest data=destin outsurv=survest;   time timeto1*eventflag(0);   strata trtcd; run;</pre>

**8.3.2. Planned Sensitivity Statistical Analyses for Time to First On-treatment Moderate/Severe Exacerbation**

**8.3.2.1. Time to First Moderate/Severe Exacerbation Including Off-treatment Data**

Secondary Statistical Analyses
Endpoint

 
Time to first moderate/severe exacerbation including off-treatment data
 

Model Specification

 
As specified in Section 8.3.1
 

Model Checking & Diagnostics

 
Refer to Appendix 10: Model Checking and Diagnostics for Statistical Analysis.
 

Model Results Presentation

 
As specified in Section 8.3.1
 
Note, only unadjusted p-values will be displayed.
 

**8.3.2.2. Time to First On-treatment Moderate/Severe Exacerbation or Premature Treatment Discontinuation**

Secondary Statistical Analyses
Endpoint

 
Time to first on-treatment moderate/severe exacerbation or premature treatment discontinuation (See Section 11.5.3.1)
 

Model Specification

 
As specified in Section 8.3.1
 

Model Checking & Diagnostics

 
Refer to Appendix 10: Model Checking and Diagnostics for Statistical Analysis.
 

Model Results Presentation

 
As specified in Section 8.3.1
 
Note, only unadjusted p-values will be displayed.
 

## 8.4. Time to First On-treatment Moderate/severe Exacerbation by Eosinophil Subgroup

Secondary Statistical Analyses
Endpoint

 
Time to first on-treatment moderate/severe exacerbation by Eosinophil Subgroup
 

Model Specification

 
Cox's proportional hazards model
 
Terms in the model: 
 
Response: time to first on-treatment, moderate/severe exacerbations
 
Categorical: treatment group, gender, exacerbation history (<math>\leq 1</math>, <math>\geq 2</math> moderate/severe), smoking status (screening), geographical region, EOS subgroup
 
Continuous: post-bronchodilator % predicted FEV1 (Screening)
 
Interaction: treatment group*EOS subgroup
 
 
 
The 'exact' method will be used for handling ties. If the analysis will not run using the 'exact' method, then the 'Efron' method for handling ties will be used instead.
 
Kaplan-Meier survivor functions will be obtained for each treatment group using PROC LIFETEST with a TIME statement.
 

Model Checking & Diagnostics

 
Refer to Appendix 10: Model Checking and Diagnostics for Statistical Analysis.
 

Model Results Presentation

 
Hazard ratios (percent reduction in risk) for pairwise treatment comparisons, within each level of eosinophil subgroup, with associated 95% CIs and unadjusted p-values will be presented.
 
The probability of having a moderate/severe exacerbation, 95% CI and first quartile and median time to exacerbation for each treatment group within each level of eosinophil subgroup will be presented.
 
The Kaplan-Meier curves will be presented showing the probability of having an event over time for each treatment group separately plotted on the same figure. This will be repeated for each level of the eosinophil subgroup. This will be repeated displaying the FF/VI and UMEC/VI treatment groups only.
 

Example SAS Code
<pre>proc phreg data=dsetin;   class trtcd smk eosinsubgroup region exachis gender;   model timeto1*eventflag(0) = trtcd gender exachis smk region eosinsubgroup pctpredFEV   trtcd*eosinsubgroup / risklimits ties=exact;   [note: contrast statements will be used for the pairwise comparisons]; run;  proc lifetest data=destin outsurv=survest;   time timeto1*eventflag(0);   strata trtcd eosinsubgroup; run;</pre>

## 8.5. Annual Rate of On-treatment Severe Exacerbations

Secondary Statistical Analyses
Endpoint(s)

 
Annual rate of on-treatment severe exacerbations
 

Model Specification, Checking & Diagnostics, Results, Presentation and SAS Code

 
This endpoints will be analyzed using the same methodology as the primary analysis of annual rate of moderate/severe exacerbations in Section 7.2
 
Note, only unadjusted p-values will be displayed.
 

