 - Double barrier method: condom and an occlusive cap (diaphragm or cervical/vault caps) with a vaginal spermicidal agent (foam/gel/film/cream/suppository)
5. **COPD Diagnosis:** An established clinical history of COPD in accordance with the definition by the American Thoracic Society/European Respiratory Society [[Celli, 2004](#)].
 6. **Smoking History:** Current or former cigarette smokers with a history of cigarette smoking of ≥ 10 pack-years at screening (visit 1) [number of pack years = (number of cigarettes per day / 20) x number of years smoked (*e.g.*, 20 cigarettes per day for 10 years, or 10 cigarettes per day for 20 years)]. Previous smokers are defined as those

who have stopped smoking for at least 6 months prior to Visit 1. *Note: Pipe and/or cigar use cannot be used to calculate pack-year history*

7. **Severity of COPD symptoms:** A score of ≥ 10 on the COPD Assessment Test (CAT) at screening.
8. **Severity of COPD Disease:** A post-albuterol/salbutamol FEV₁/FVC ratio of < 0.70 at Screening.
9. **Existing COPD maintenance treatment:** Subject must be receiving daily maintenance treatment for their COPD for at least 3 months prior to Screening.
Note: Subjects receiving only PRN COPD medications are not eligible.
10. **History of Exacerbations:** Subjects must demonstrate:
a post-bronchodilator FEV₁ $< 50\%$ predicted normal and a documented history of ≥ 1 moderate or severe COPD exacerbation in the previous 12 months

OR

a post-bronchodilator $50\% \leq \text{FEV}_1 < 80\%$ predicted normal and a documented history of ≥ 2 moderate exacerbations or a documented history of ≥ 1 severe COPD exacerbation (hospitalized) in the previous 12 months.

Note: *Percent predicted will be calculated using the European Respiratory Society Global Lung Function Initiative reference equations [Quanjer, 2012].*

Note: *A documented history of a COPD exacerbation (e.g., medical record verification) is a medical record of worsening COPD symptoms that required systemic/oral corticosteroids and/or antibiotics (for a moderate exacerbation) or hospitalization (for a severe exacerbation). Prior use of antibiotics alone does not qualify as an exacerbation history unless the use was associated with treatment of worsening symptoms of COPD, such as increased dyspnea, sputum volume, or sputum purulence (color). Subject verbal reports are not acceptable.*

11. **Liver function tests:**

- alanine aminotransferase (ALT) $< 2x$ upper limit of normal (ULN);

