8.3.5. Key Elements of Analysis Plan

8.3.5.1. Efficacy Analyses

The primary efficacy endpoint of the annual rate of on-treatment moderate and severe exacerbations will be analyzed using a generalized linear model assuming the negative binomial distribution, with the logarithm of time on treatment as an offset variable. The model will include terms for treatment group, gender, exacerbation history (one, two or more), smoking status at screening, baseline disease severity (as % predicted FEV₁) and geographical region. The adjusted mean annual rates, pair-wise treatment ratios and associated p-values and confidence limits will be presented. The fit of the negative binomial model will be examined using “Q-Q” plots of standardized residuals with simulated envelopes.

For the co-primary endpoints, sensitivity analyses will be performed where all available data collected until the time of study withdrawal will be used. For these sensitivity analyses, the total number of events and the total time in the study (both on-treatment and post-treatment) prior to study withdrawal will be used in the analysis model. Imputations made for the period following study withdrawal will be described in the RAP. Additional sensitivity analyses using multiple imputation methods will be described in the RAP.

The secondary endpoints of trough (pre-dose AM) FEV₁ and SGRQ total score will be analysed using mixed models repeated measures with covariates of treatment group, smoking status at screening, baseline, region, and visit, plus interaction terms for visit by baseline and visit by treatment group.

The secondary endpoints involving time to first moderate and/or severe exacerbation will compare the treatment groups using Cox's proportional hazards model, adjusting for treatment group, gender, exacerbation history (one, two or more), smoking status at screening, baseline disease severity (as % predicted FEV₁), and geographical region.

Secondary and other endpoints involving the annual rate of exacerbations will be analysed as described for the primary endpoint.

The additional endpoint of time to onset of multiple moderate and severe exacerbations will be analysed using an Anderson-Gill model for time to recurrent events.

Full details of the analyses to be performed on all primary, secondary and other efficacy endpoints will be given in the RAP.

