**7.2. Planned Primary Statistical Analyses for Primary Endpoint**

Primary Statistical Analyses
Endpoint(s)

 
• Annual rate of on-treatment moderate/severe exacerbations comparing FF/UMEC/VI with FF/VI
 
• Annual rate of on-treatment moderate/severe exacerbations comparing FF/UMEC/VI with UMEC/VI
 

Model Specification

 
• Generalized linear model assuming a negative binomial distribution
 
• Terms in the model:             
 
• Response: number of recorded, on-treatment, moderate/severe exacerbations experienced per subject.
 
• Categorical: treatment group, gender, exacerbation history (<math>\leq 1</math>, <math>\geq 2</math> moderate/severe), smoking status (screening), geographical region
 
• Continuous: post-bronchodilator % predicted FEV1 (Screening)
 
• Offset: As defined in Section 11.5.3.1
 
 
 

Model Checking & Diagnostics

 
• Refer to Appendix 10: Model Checking and Diagnostics for Statistical Analysis
 

Primary Statistical Analyses
Model Results Presentation

 
Treatment group model estimated exacerbation rates and associated 95% confidence intervals (CI), pairwise treatment rate ratios and associated 95% CIs will be presented. The pairwise treatment percent reductions in annual exacerbation rate and associated 95% CIs will also be presented in the same table.
 
Both adjusted (accounting for the Hochberg multiplicity adjustment, see Section 11.9) and unadjusted p-values will be presented for the pairwise treatment comparisons of FF/UMEC/VI versus FF/VI, FF/UMEC/VI versus UMEC/VI. Unadjusted p-values will be presented for UMEC/VI versus FF/VI.
 
The pairwise treatment rate ratios and associated 95% CIs for FF/UMEC/VI versus FF/VI and FF/UMEC/VI versus UMEC/VI will also be presented graphically
 

Example of SAS Code
<pre>proc genmod data=dsetin;   class trtcd gender exachis smk region;   model no_exac = trtcd gender exachis smk pctpredFEV region     / dist=negbin link=log offset=log_tm wald type3;   [note: both contrast and estimate statements will be used for the pairwise comparisons]   lsmeans trtcd / cl diff om; run;</pre>

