**11.5.2.8. COPD Exacerbation History****COPD Exacerbation History**

- Individual exacerbations during the 12 months prior to Screening and during the study were to be collected on the eCRF by the Investigator.
- COPD exacerbations with onset date on or after the date of Screening will not be included in the counts of number of exacerbations in the past year; all other exacerbations recorded on the eCRF will be included in the counts, even if onset/resolution dates are missing or earlier than the start of the exact 12 month period prior to Screening.
- COPD exacerbations reported in the past 12 months will be categorized as 0, 1, 2,  $\geq 3$  and a separate category of  $\geq 2$ .
- Number of COPD exacerbations reported in the past 12 months prior to Screening will be summarized according to three categories: moderate COPD exacerbations, severe COPD exacerbations and moderate/severe COPD exacerbations. Exacerbation severity is defined in Section [11.5.3.1](#).
- Total number of moderate/severe COPD exacerbations are defined as total numbers of moderate and severe COPD exacerbations for each subject.
- Summaries of moderate/severe exacerbations by treatment course are defined as exacerbations treated with systemic/oral corticosteroids (with or without antibiotics), and exacerbations treated with antibiotics (with or without systemic/oral corticosteroids).

**11.5.2.9. Screening Lung Function and GOLD Grade****Screening Lung Function****Pre-bronchodilator FEV1/FVC, FEV1 Percent Predicted and Reversibility**

- Pre-bronchodilator FEV1/FVC ratio and pre-bronchodilator FEV1 as a percentage of predicted normal at Screening are not collected in the eCRF and will be calculated as:
  - Pre-bronchodilator FEV1/FVC = Pre-bronchodilator FEV1/Pre-bronchodilator FVC
  - Pre-bronchodilator Percent Predicted = (Pre-bronchodilator FEV1/Predicted FEV1) \* 100
- The reversibility to salbutamol status of a subject is calculated at Screening and is based on the

Screening Lung Function
Pre-bronchodilator FEV1/FVC, FEV1 Percent Predicted and Reversibility

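### The severe-exacerbation rate model has no term for prior hospitalised exacerbations, although they are collected and counted; adding one is a small, free gain in precision

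*SAP*

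**What the plan says.** The annual rate of severe exacerbations is a secondary endpoint for both comparisons (Protocol 6.2.2). SAP 8.5 analyses it "using the same methodology as the primary analysis of annual rate of moderate/severe exacerbations in Section 7.2". The SAP 7.2 model statement is "model no_exac = trtcd gender exachis smk pctpredFEV region", where the history variable has two levels: at most one, or at least two, moderate/severe events. The severe rate by eosinophil subgroup (SAP 9.1.2.3, through 8.6) carries the same term. The protocol lays down this reuse in 8.3.5.1: "Secondary and other endpoints involving the annual rate of exacerbations will be analysed as described for the primary endpoint".

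SAP 11.5.2.8 builds the history total as moderate plus severe events, unweighted. It also says that the number of events in the 12 months before screening "will be summarized according to three categories: moderate COPD exacerbations, severe COPD exacerbations and moderate/severe COPD exacerbations". The separate severe count is used only for description.

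Under inclusion criterion 10 (Protocol 4.2), a subject with FEV1 below 50% predicted needs at least one moderate or severe event. A subject with FEV1 50 to <80% needs at least two moderate events or "a documented history of ≥ 1 severe COPD exacerbation (hospitalized) in the previous 12 months".

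**The concern.** A history term built for moderate/severe events is carried over to an endpoint that counts hospitalisations only. The baseline measure closest to that endpoint, a hospitalised exacerbation in the previous year, is available for every subject and left out. Protocol 1.1 notes that the 2013 GOLD update treats a hospitalised exacerbation as a marker of high risk, so it is reasonable to expect it to be prognostic.

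The eligibility rule makes the gap systematic. One group enters only because of a hospitalisation, yet the model sees a low event count and a better FEV1. At stake is the precision of both severe-exacerbation comparisons, one of which uses the 2,000-subject UMEC/VI arm. Neither document states power for this endpoint.

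**Working it through.** **1. Who shares a level.** Criterion 10 crossed with the SAP coding gives:

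| FEV1 % predicted | History level | No prior severe event | Prior severe event |
|---|---|---|---|
| <50 | ≤1 | eligible | eligible |
| <50 | ≥2 | eligible | eligible |
| 50 to <80 | ≤1 | **not eligible** | eligible |
| 50 to <80 | ≥2 | eligible | eligible |

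Seven cells can occur. At FEV1 50 to <80%, level ≤1 implies a prior hospitalisation. At FEV1 <50%, level ≤1 mixes single-moderate with single-severe subjects. An additive model in FEV1 and history recovers only part of this.

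**2. The plan's own figures.** None exist for severe exacerbations. For the primary endpoint, take variance = (1/λT + k)/nT + (1/λD + k)/nD, with k = 0.75, λT = 0.80 and two-sided α = 0.01 (Protocol 8.2.1).
- Against FF/VI (λD = 0.80/0.88): SE = √(2.00/4000 + 1.85/4000) = 0.0310. Power = Φ(0.1278/0.0310 − 2.576) = 93.9%; the protocol states 90%.
- Against UMEC/VI (λD = 0.80/0.85): SE = √(2.00/4000 + 1.8125/2000) = 0.0375. Power = Φ(0.1625/0.0375 − 2.576) = 96.1%; the protocol states 92%.

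With an unstated mean exposure of about 0.80 year, all 24 cells of Tables 5 and 6 reproduce within about 1 to 1.5 points. The stated powers are on the cautious side and do not bear on this point.

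**3. Effect of adding the term.** Every severe-event input is an assumption: control rate 0.10 to 0.25 per year, rate ratio for a prior severe event 1.5 to 3, dispersion 0.75 to 2, 14% to 44% with a prior severe event, treatment rate ratio 0.80. FEV1 (dichotomised at 50%) and history were given rate ratios of 1.4 and 1.3. Negative binomial models were fitted over the seven cells with and without the term. Power = Φ(0.2231/SE − 1.96). Rows below have 28% with a prior severe event.

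| Arms | Rate | Ratio | k | SE without → with | Variance | Power |
|---|---|---|---|---|---|---|
| 4000:2000 | 0.10 | 1.5 | 0.75 | 0.0935 → 0.0934 | −0.3% | 66.5 → 66.6% |
| 4000:2000 | 0.15 | 2 | 0.75 | 0.0783 → 0.0777 | −1.4% | 81.3 → 81.9% |
| 4000:2000 | 0.15 | 2 | 2 | 0.0846 → 0.0840 | −1.3% | 75.1 → 75.7% |
| 4000:2000 | 0.25 | 3 | 0.75 | 0.0648 → 0.0629 | −5.7% | 93.1 → 94.4% |
| 4000:4000 | 0.15 | 2 | 0.75 | 0.0650 → 0.0646 | −1.4% | 93.0 → 93.3% |

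Percentages come from unrounded standard errors. Over the whole range at 4000:2000, variance falls by 0.2% to 5.7%, the standard error by 0.1% to 2.9%, and power rises by 0.1 to 1.6 points. The treatment estimate was −0.2231 = ln 0.80 with and without the term.

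**4. Why it is small.** In the middle case, omitting the term raises the fitted dispersion from 0.75 to 0.95. With arm rates 0.12 and 0.15, the 1/rate terms are 8.33 and 6.67 and dominate: √((8.33 + 0.95)/4000 + (6.67 + 0.95)/2000) = 0.0783. With 0.75 in place of 0.95 the same formula gives 0.0773. The fitted value is 0.0777 because the formula ignores variation in rate between subjects.

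**5. Time to first severe event.** One Cox scenario (ratio 2.5, 60 simulated trials of 6,000) gave a standard-error ratio of 1.000. The mean coefficient moved from −0.217 to −0.219 and mean |z| from 2.94 to 2.97.

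**The case against.** The strongest reply is that nothing is broken. Reuse of the primary model is pre-specified, the two documents agree, and randomisation protects the comparison whatever baseline terms are left out. One covariate set across exacerbation definitions also makes their rate ratios easy to compare. The endpoint lies outside the two-block hierarchy (SAP 11.9), is reported with unadjusted p-values, and has no precision target. The gain rests on a prognostic ratio that the documents never give: Protocol 1.1 lists hospitalisation as one of several routes into the same high-risk class and does not rank it as the better predictor of hospitalisation.

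All of that stands, and it keeps the point small. It shows that the planned analysis is valid, not that it is as precise as the collected data allow.

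A reader might also infer that the adjustment pushes the wrong way for the FEV1 50 to <80% group. The documents do not support this. The history and FEV1 coefficients are estimated from the severe-event data, so no direction is imposed, and the eligibility link lets those two terms carry part of the information. Nor are all previously hospitalised subjects coded low: one who also had a moderate event counts as two and falls in the upper level.

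**Conclusion.** The point holds as a minor efficiency improvement. Subjects whose only prior event was a hospitalisation are pooled with subjects who had one moderate event, and the separately counted severe history is not modelled. If prior hospitalisation is prognostic, the rate model may understate risk in that group and loses some precision: about 0.2% to 5.7% of the variance of the log rate ratio, 1.4% in the middle case, and under 2 points of power. Those figures depend wholly on the assumed rate, ratio, dispersion and prevalence; the true size cannot be had from the documents.

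Two further inferences are not supported. The omission does not bias the treatment rate ratio: treatment is randomised, and the fitted ratio was the same with and without the term. Nor does the precision claim extend to the Cox and Andersen-Gill analyses: the single Cox scenario showed no fall in standard error, and the Andersen-Gill model was not checked.

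**What to change.** Before unblinding, add prior severe exacerbation in the past 12 months (0, ≥1) as a categorical covariate to the severe-exacerbation negative binomial models: SAP 8.5, and the severe rate by eosinophil subgroup in 9.1.2.3. Keep all existing terms. If the team prefers to hold the planned model as the main analysis, the extended model can be a pre-specified supportive analysis.

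The same term may go into the severe-only time-to-event models (SAP 9.1.2.1, 9.1.2.2 and 9.1.2.4) for consistency, without claiming a smaller standard error there. Leave the non-severe endpoints in 9.1.2.1, 9.1.2.3 and 9.1.2.4 unchanged.

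The cost is one model term from a variable already derived under SAP 11.5.2.8, where events with missing dates still count, plus an entry in SAP 2.1, because Protocol 8.3.5.1 ties secondary rate endpoints to the primary model. No new data are needed.
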